Serious Adverse Event Reporting Children's Health and Environment Program, (CHEP)
Child Health Research Centre
[contact]

2. Investigator Signature Page

Reducing acute severe respiratory events in health care workers during the Covid-19 pandemic with OM85

I confirm that I have read **Protocol Version 2.0 dated 12th June 2020**. As the site investigator, I understand it, and I agree to adhere to the study conduct requirements and agree to conduct this protocol in accordance with International Conference on Harmonization Good Clinical Practice E6 (ICH-GCP), the Declaration of Helsinki, the United States (US) Food and Drug Administration (FDA), and local regulations and guidelines. I agree to report all information or data in accordance with the protocol and in particular I agree to report any serious adverse events. I will accept the monitors, auditors and regulatory inspector's oversight of the study. I will promptly submit the protocol to the applicable ethical review board.

Chief investigator signature

[name] [name]

Chief investigator printed name

Date

This page has been left blank intentionally

3. Synopsis of Protocol

Title	A phase 3, multi-centre study testing the reduction of acute severe respiratory events in health care workers during the Covid-19 pandemic with OM85
Clinical phase	Phase Three
Protocol number	BV-2020/19
Principal Investigators	[name] [name] [name] Assoc [name] [name] [name] [name] Assoc [name] [name] [name]
Statistical consultant	[name]
Study design	Parallel group, Wait-list design, with treatment delayed for 3 months Participants will be randomized on a 1:1 ratio with 500 participants per group in Australia and 500 per group in the UK. Group 1: Wait-list control. One capsule OM85 (7.0 mg) will be given daily for 3 months, commencing in Month 3, with 3 months follow-up off treatment. Group 2: Initial treatment. One capsule OM85 (7.0 mg) will be given daily for 3 months, commencing on day 0, with 3 months follow-up off treatment.
Accrual objective	2000 Health Care Workers (HCW):- 1000 from Brisbane Hospitals 1000 from UK Hospitals

Accrual period	4 weeks
Study duration	12 months
Countries	Australia, United Kingdom
Sites	Queensland Children’s Hospital, Brisbane (Site Investigator: [name]) Imperial College Hospital, London (Site Investigator: [name]) Prince Alexandra Hospital, Brisbane (Site Investigator: [name]) Princess Charles Hospital, Brisbane (Site Investigator: Assoc [name])
Primary endpoint	The proportion of HCW contracting an ARI necessitating workforce removal.
Secondary endpoints	
Secondary endpoints include:
 
 • The time to ARI necessitating workforce removal • The proportion of HCW contracting an ARI necessitating workforce removal at end of treatment and at the end of the follow-up period, overall and by department • The total number of days with respiratory symptoms (upper or lower) • The proportion of HCW with COV infection documented by PCR, seroconversion and/or COV ARI necessitating workforce removal. • The time to LRI necessitating workforce removal • The proportion of HCW contracting an LRI necessitating workforce removal at end of treatment and at the end of the follow-up period, overall and by department • The proportion of HCW with COV infection documented by PCR, seroconversion and/or COV LRI necessitating workforce removal.
Mechanistic endpoints	
Mechanistic endpoints (Brisbane only) include:
 
 • Seroconversion to COV • Host immune cell profile grouped who test respectively positive or negative to COV during a ARI and stratified by treatment (COV⁺/OM⁺, COV⁺/OM⁻, COV⁻/OM⁺, COV⁻/OM⁻).

- White blood cell transcriptomic profile by group (COV⁺/OM⁺, COV⁺/OM⁻, COV⁻/OM⁺, COV⁻/OM⁻).
- White blood cell cytokine production profile by group (COV⁺/OM⁺, COV⁺/OM⁻, COV⁻/OM⁺, COV⁻/OM⁻).

Safety endpoints	
Safety endpoints include:
 
 • Treatment-related adverse events • Routine haematology and clinical chemistry
Inclusion criteria	
Participants who meet all of the following criteria are eligible for enrolment:
 
 1. HCW “front line” clinical departments assessing or caring for patients with suspected or proven COV infection at one of the recruiting hospitals in Brisbane or London 2. Participants who, in the opinion of the investigator, are able to comply with the protocol for its duration 3. Written informed consent signed and dated by participant according to local regulations
Exclusion criteria	
Participants who meet any of these criteria are not eligible for enrolment:
 
 1. Staff with prior COV infection necessitating workforce removal.
Treatment description	Broncho-Vaxom adult capsules® (OM85)

mg	milligrams
MPV	Mean platelet volume
PA	Princess Alexandra Hospital, Brisbane
PPE	Personal protective equipment
QCH	Queensland Children's Hospital, Brisbane
QH	Queensland Health
SAE	Serious adverse events
SAP	Statistical analysis plan
sLRI	Severe lower respiratory infection
SPT	Skin prick test
TGA	Therapeutic Goods Administration
TKI	Telethon Kids Institute
TPCH	The Prince Charles Hospital, Brisbane
UQ	University of Queensland
UV	Unscheduled visit
WLC	Wait List Control

6. Introduction

6.1 Background

6.1.1 Covid-19

The Covid-19 pandemic has been characterised by acute respiratory distress syndrome (ARDS) accompanied by a systemic cytokine-storm resulting in severe illness, respiratory failure and death in some. SARS-Cov-2 (COV) infection *per se* is not the only underlying issue here, as it is becoming evident that ARDS is relatively rare amongst infected subjects, and appears to be associated with gross dysregulation of ensuing host-anti-viral responses resulting in collateral immune-inflammatory-mediated damage to host tissues. Rather than waiting for susceptible subjects to present with COV-associated ARDS, we propose treatment of healthy health care workers (HCW) with a therapeutic agent which simultaneously targets front-line innate anti-viral immune defences, together with the core mechanism that controls immune response intensity in the airways. This research addresses the hypothesis that resistance to development of severe COV-associated respiratory disease in front-line health workers, even in those who develop a primary infection, can be boosted via a regimen of daily dosing with the bacterial-derived immunomodulatory agent OM85.

6.1.2 Health Care Workers

HCW are at the forefront of the Covid pandemic. Figures from China show around 3300 HCW were infected, as were 20% of Italy's HCW¹. Infected HCW who develop lower respiratory illnesses (LRI) are removed from frontline services putting additional pressure on system ability to provide patient care. Respiratory viruses, including COV, are initially encountered by the nasal epithelium where infection is initiated. An adequate anti-viral response can contain the virus in the upper airway, with cold-like symptoms. An inadequate response can see the infection spreading to the lower respiratory tract and induce a severe lower respiratory illness (sLRI). HCW in front line clinical departments, such as emergency departments, intensive care units, COV isolation wards and radiology departments, are at increased risk of COV infection.

6.1.3 Personal Protective Equipment

In theory, personal protective equipment (PPE) can protect HCW from infection. However, adequate PPE is in short supply and commonly used surgical masks are unlikely to protect HCW from virus-containing aerosols generated by infectious patients. Facemasks, originally introduced to protect patients from respiratory emissions from surgeons, can protect the wearer from inhaling particulate matter². However, even the most efficient mask is unlikely to give adequate protection if not worn correctly, or if the mask does not fit³. Winter et al.³ tested the fit of three versions of the high-efficiency N95 respirator (commonly known as P2 in Australia) to 50 health care workers. They found that only 18% of health care workers achieved an adequate fit without training, 40% achieved an adequate fit after training, and adequate mask fit was not possible in 28% of subjects. These data show that assuming that a mask will provide protection is likely to be false in many circumstances, especially in the absence of adequate training. N95 respirators are certified against national standards (USA), providing at least 95% protection against particles in the sub-micron (0.1 to 0.3µm) range⁴. N99 masks, that filter 99% of sub-micron particles, odours and gaseous pollutants, and >99% of bacteria and viruses are likely to be required to adequately protect HCW from COV-infected patients.

Most HCW rely on surgical masks that usually have a layer of 3-ply melt-blown material between layers of non-woven fabric. The melt-blown material acts as the filter that stops

microbes from entering or exiting the mask. Most surgical masks feature pleats or folds allowing the user to expand the mask to cover the area from the nose to the chin. The mask may have a metal strip the user moulds across the bridge of the nose to improve the fit, and is fixed to the face by elastic ear loops or ties secured behind the head. These masks are not designed to form a seal around the nose and mouth nor to protect the wearer from submicronic particulate matter⁵, including viruses such as COV.

6.1.4 Therapeutic options

As the PPE available to HCW is unlikely to prevent COV infection, an alternative approach is required. OM85, variably known as Broncho-Vaxom®, Broncho-Munal®, Ommunal®, Paxoral®, or Vaxoral®, has been in widespread clinical use throughout Europe and South America since the early 1980s for protection of infants, children and adults from the inflammatory sequelae of lower respiratory diseases, in clinical settings ranging from infection-associated wheeze in infants and school children^{6,7} to severe winter exacerbations occasioning hospitalization in adult COPD patients^{8,9}. While its mechanism-of-action is not fully understood, the accumulating body of clinical and experimental/mechanistic data has been sufficient to attract major support from regulators and funding agencies, exemplified by the US NIH-funded ORBEX RCT (NCT02148796) and NHMRC-funded OMPAC RCT (ACTRN12612000518864)⁷ which both target ARIs in children.

Evidence from numerous trials has demonstrated that OM85 treatment during periods of high infection risk can reduce the frequency of symptomatic ARI^{10,11}. The mechanism-of-action appears to involve reduction in susceptibility to upper respiratory infection and attenuation of the intensity of inflammation-associated symptoms that accompany infection spread to the lower airways. Clinical experience with OM85 indicates it is active against a wide spectrum of microbial pathogens. As such, it is likely to target immunoregulatory pathways that are fundamental to anti-microbial immunity¹⁰, particularly those which control the intensity of host defence-associated inflammatory responses. Accumulating evidence relating to COV pathogenesis suggests that primary infection followed by successful clearance represents the norm, with relatively rare severe infection-triggered events being associated with uncontrolled/excessive local and systemic inflammatory responses. Based on its performance in other infection-related settings^{6,10}, we hypothesize that OM85 pre-treatment has the capacity to enhance resistance to primary infection with COV, but more importantly to stabilize immunoregulatory mechanisms that maintain immune homeostasis during COV infection and lessen risk for progression to severe life-threatening symptoms.

6.2 Investigational product

OM85 (commercial name Broncho-Vaxom adult capsule) consists of a capsule containing 7.0mg of active bacterial soluble fractions in one dose. Investigational product is to be taken orally daily for 3 months

6.3 Known and potential risks

Published clinical trials have reported OM85 to be well tolerated in children and adults. Reports of discontinuation of drug with an adverse event have been reported in three studies; two children from two separate studies discontinued drug due to rash or diarrhoea, and a study in adults with chronic obstructive pulmonary disease or chronic bronchitis reported 5 participants

in the active group (n=142) and 9 participants in the placebo group (n=131) discontinuing investigational product. In most clinical trials the number of participants experiencing adverse events were no different between the active (OM85) and placebo groups¹². In adults, the most common reported adverse events were gastrointestinal, including nausea and diarrhoea. Six studies reported no adverse events. In elderly patients (>65 years), the most common adverse events were disease of the genitourinary (19/147, 13%), “symptoms, signs and ill-defined conditions” (11/147, 7%) and disease of the circulatory system (7/147, 5%).

6.4 Study population

The study population will include Health Care workers (adults) in emergency departments, radiology departments, isolation wards, intensive care units or other “front line” clinical departments of major Brisbane hospitals (CHQ, PA, TPCH) in Australia and at UK Hospitals

7. Study objectives and purpose

7.1 Primary objective

To reduce the proportion of HCW contracting an ARI necessitating workforce removal.

7.2 Secondary objectives

The secondary objectives of this study are to assess whether treating “front line” HCW at high risk of ARI, including LRI, with COV infection:

- Decreases time to ARI, including LRI, necessitating workforce removal
- Reduces the proportion of HCW contracting an ARI, including LRI, necessitating workforce removal at end of treatment and at the end of the follow-up period, overall and by department.
- Reduces the total number of days with respiratory symptoms (upper or lower)
- Reduces the proportion of HCW with COV infection documented by PCR, seroconversion and/or COV ARI, including LRI, necessitating workforce removal.

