8.2.2 Secondary efficacy endpoints

Secondary endpoints include:

- The time to ARI necessitating workforce removal
- The proportion of HCW contracting an ARI necessitating workforce removal at end of treatment and at the end of the follow-up period, overall and by department
- The total number of days with respiratory symptoms (upper or lower)
- The proportion of HCW with COV infection documented by PCR, seroconversion and/or COV ARI necessitating workforce removal.
- The time to LRI necessitating workforce removal
- The proportion of HCW contracting an LRI necessitating workforce removal at end of treatment and at the end of the follow-up period, overall and by department
- The proportion of HCW with COV infection documented by PCR, seroconversion and/or COV LRI necessitating workforce removal.

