13.2 Sample size calculations

There are no data in the literature on use of OM85 for the primary prevention of ARI, in relation to COV. However, 20% of Italy's HCW are infected with COV¹. If we assume 20% infection in Gp 1, then with 500 HCW in each group we will be able to detect a reduction in ARI in Gp 2 by 32.5% (to 13.5%) with 80% power ($\alpha=0.05$). Combined with 1000 UK-recruited HCW, we will be able to detect a 25% reduction (80% power, $\alpha=0.05$).

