13.2.2 Statistical analyses

The *interim analysis*, undertaken at month 1 on both the "intention-to-treat" and "per protocol" groups, will examine the primary outcome: if the treatment difference is statistically significant in favour of OM85 the DSMB will consider immediately switching WLC participants to OM85.

Between-group differences in the primary outcome at 3 months will be assessed using log-binomial regression. Secondary outcomes measured to follow-up cessation will be assessed using mixed-effects models with group and stage (treatment/follow-up) (main effects and interaction) as fixed effects and HCW as random effect. Time-to-ARI analyses will use the log-rank test. Analyses will be undertaken on both the "intention-to-treat" and "per protocol" groups.

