13.3.2 Secondary efficacy endpoints and mechanistic endpoints

The secondary endpoints, defined in Section 7.2.2, and mechanistic evaluations, defined in Section 7.2.3, will be assessed using mixed-effects models with group and stage (treatment/follow-up) (main effects and interaction) as fixed effects and HCW as random effect. Time-to-ARI, including LRI, analyses will use the log-rank test.

These analyses will be undertaken, on both the “intention-to-treat” and “per protocol” groups, regardless of the outcome of the primary endpoint analysis.

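### Time to ARI and time to LRI are planned as a log-rank test alone, with no effect estimate, strata or time window, and the matching objective in 7.2 is worded in the wrong direction

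*Combined protocol and SAP*

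**What the plan says.** The secondary objectives (7.2) ask whether treatment "Decreases time to ARI, including LRI, necessitating workforce removal". The primary objective (7.1) is "To reduce the proportion of HCW contracting an ARI necessitating workforce removal", and the other three bullets in 7.2 each look for a reduction in a bad outcome. The rationale in 6.1.4 supposes that "OM85 pre-treatment has the capacity to enhance resistance to primary infection with COV". The endpoint list (8.2.2) has no direction: "The time to ARI necessitating workforce removal", with a parallel line for LRI.

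The analysis is one sentence, given twice. Section 13.2.2: "Time-to-ARI analyses will use the log-rank test". Section 13.3.2: "Time-to-ARI, including LRI, analyses will use the log-rank test". Neither names an estimate, an interval, strata or a cut-off date.

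Three other sections bear on this:
- Section 13.1 stratifies randomisation by country, hospital and department risk.
- Section 13.3.1 restricts the primary endpoint to data gathered before the wait-list group goes on to OM85.
- Section 10.2 starts wait-list treatment at month 3 and follows Group 2 to month 6 and Group 1 to month 9.

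**The concern.** Taken literally, the objective describes harm: a shorter time to ARI means that workers fall ill sooner. The word should be corrected, but nothing is computed from it.

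The analysis sentence matters more. A log-rank p-value says whether two curves differ, not by how much, so the plan commits to no effect size on the time scale for either endpoint. It does not carry the stratified randomisation into the test. It also leaves open whether events after month 3 count. From then on the wait-list group takes OM85 and Group 2 is off it, so the comparison is no longer treated against untreated. A comparison run to the end of follow-up could lose most of a real effect.

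**Working it through.** **Inputs.** Section 13.2 states for Australia: "with 500 HCW in each group we will be able to detect a reduction in ARI in Gp 2 by 32.5% (to 13.5%) with 80%". Here the 80% is the power, and the control rate is 20%. For both countries together the section adds: "Combined with 1000 UK-recruited HCW, we will be able to detect a 25% reduction". That is 20% vs 15% with 1000 per group. Alpha is 0.05; I assume two-sided. I also assume a constant hazard within each 3-month stage and no dropout. The documents give no LRI rate, so only ARI can be sized.

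**1. The plan's own figure.** With pooled variance, power = Φ([d√n − 1.96√(2p̄q̄)] / √(p1q1 + p2q2)).
- 500 per group: (0.065 × 22.361 − 1.96 × 0.5281) / 0.5261 = 0.795, so power is 78.7% against the stated 80%.
- 1000 per group, 20% vs 15%: 83.8%.

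The stated design reproduces to within rounding.

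**2. Direction.** Monthly hazard λ = −ln(1 − p)/3, which is 0.0744 for 20% and 0.0483 for 13.5%. Mean ARI-free time over 3 months is p/λ: 0.20/0.0744 = 2.69 months on wait-list and 0.135/0.0483 = 2.79 on OM85. Benefit is an increase in time to ARI.

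**3. What the test shows.** Take Z ≈ (O − E)/√(events/4), with E as half of all events. At 500 per group, benefit is 67.5 vs 100 events: (67.5 − 83.75)/√(167.5/4) = −2.51. The mirror-image harm gives +2.51. Chi-square is 6.31 both times. The signed statistic separates the two cases; the chi-square and two-sided p-value do not, and neither gives a size.

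**4. The missing estimate.** HR = ln(1 − p2)/ln(1 − p1), with interval exp(ln HR ± 1.96 × 2/√events).
- 500 per group: HR 0.65, 167.5 events, CI 0.48 to 0.88.
- 1000 per group: HR 0.73, 350 events, CI 0.59 to 0.90.

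**5. The window.** Suppose first events are counted to month 6. At month 3, 500 × 0.80 = 400 wait-list and 500 × 0.865 = 432.5 Group 2 workers are event-free. The wait-list group then has 400 × 0.135 = 54 events on OM85. For Group 2 I take two extremes:
- The effect persists off treatment: 432.5 × 0.135 = 58.4 events. The HR in this stage is 1, and the stage adds 112.4 events.
- The effect ends with treatment: 432.5 × 0.20 = 86.5 events. The HR is inverted, and the stage adds 140.5 events. Both groups then reach 1 − 0.80 × 0.865 = 30.8% by month 6.

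Weighting ln HR by events, with ln 0.65 = −0.431:
- Persists: −0.431 × 167.5/279.9 = −0.258, HR 0.77.
- Ends: −0.431 × (167.5 − 140.5)/308 = −0.038, HR 0.96.

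Power is Φ(|ln HR| × √events/2 − 1.96). The same steps with 1000 per group (ln HR −0.317) give the right-hand columns.

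| Window | 500/group: events, HR, power | 1000/group: events, HR, power |
|---|---|---|
| To month 3 | 167.5, 0.65, 80% | 350, 0.73, 84% |
| To month 6, effect persists | 279.9, 0.77, 58% | 597.5, 0.83, 62% |
| To month 6, effect ends | 308, 0.96, 5% | 640, 0.97, 6% |

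Month 6 for Group 2 is from 10.2. Appendix 1 prints Day 120 for that visit; a shorter window would dilute less.

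**6. Strata.** Three Brisbane hospitals by two risk levels make 6 strata, or about 167.5/6 = 28 events each if evenly spread. Adding the one London hospital in the synopsis makes 8, or 350/8 = 44 each. A stratified Cox model is workable.

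**The case against.** The strongest reply is that little hangs on this. The intended direction is plain from 7.1, 6.1.4 and the adjacent bullets, and 13.3.2 refers to the endpoints, which are worded neutrally, rather than to the objectives. No analyst would report earlier illness as success. The log-rank sentences are silent on estimates but do not exclude them, and the 3-month log-binomial regression already yields a risk ratio for the same ARI event. A stratified Cox model is only one of several reasonable choices.

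Most of that stands, and it rules out some stronger readings:
- A reader might infer that a success criterion has been reversed. The documents set no success criterion or decision rule for secondary endpoints.
- A reader might infer that the log-rank method has no direction. The sign of observed minus expected shows it (step 3); only the two-sided p-value lacks it.
- A reader might infer that the plan will pool events after month 3. It does not say so. It sets no window, and step 5 shows the consequence if the longer one were used.

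The reply does not remove the gap. Being silent on an estimate is not committing to one, the risk ratio is not on the time scale, and 13.3.1 limits only the primary endpoint to the period before wait-list treatment.

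**Conclusion.** The point holds as a minor one. The objective in 7.2 is worded backwards and should be corrected, with no effect on any analysis. The log-rank sentences in 13.2.2 and 13.3.2 leave both time-to-event endpoints without a planned effect size, strata or window.

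The window has the largest consequence. At 500 per group, an HR of 0.65 to month 3 would be averaged to between 0.77 and 0.96 by month 6, and power would fall from about 80% to between 58% and 5%. That range rests on a constant hazard, no dropout, the protocol's 20% and 13.5%, and the two extremes for how long the effect lasts. The cost of ignoring the strata cannot be computed, because no rates by hospital or department are given; I would expect some loss of precision and no false positives. The primary analysis, sample size and power are untouched.

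**What to change.** 1. In 7.2, replace 'Decreases' with 'Increases (delays)'.
2. In 13.2.2 and 13.3.2, make the log-rank test for time to ARI and time to LRI stratified by the randomisation factors in 13.1.
3. Alongside it, report a hazard ratio (OM85 vs wait-list) with 95% CI from a Cox model with the same strata, stating that a ratio below 1 favours OM85.
4. State that both use data from Day 0 until the wait-list group starts treatment (about Day 90), as 13.3.1 does for the primary endpoint. Tying the cut to the start of wait-list treatment also covers an early switch after the month 1 interim analysis.

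The cost is a word, a few lines of text and one standard model, with no new data collection. Later events drop out of this comparison (112 to 141 of them at 500 per group in step 5), but they do not compare OM85 with no treatment. The mixed-effects models with group and stage still cover the follow-up period for the other secondary endpoints.
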